8.2 Clinical laboratory evaluation

Analysis of clinical laboratories data will be performed by treatment for Hematology and Biochemistry tests. In case of different units of measure considered for the same laboratory parameter, all values will be converted into SI units (if applicable) or to the same unit.

The following summaries will be provided:

- A summary table showing for all laboratory tests the values and changes from baseline to each subsequent time points;
- A summary table showing for all laboratory tests the frequency of subjects reporting laboratory values out of normal range (yes, no) at baseline and at subsequent time points.

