## 9.4.3 Safety Analysis

Treatment-Emergent Adverse Events (TEAEs), Adverse Drug Reactions (ADRs) and Serious Adverse Events (SAEs) will be presented treatment arm (and route of administration if required) in terms of number of AEs and their incidence by System Organ Class (SOC) and Preferred Terms (PT) using MedDRA. Analyses will be provided also by severity and relationship to the treatment. Vital signs and laboratory tests will be presented using descriptive statistics at each available visit. Additionally, the frequency of subjects reporting an abnormal or abnormal clinically significant laboratory value at each available visit will be presented for each laboratory parameter. Shift tables versus baseline will compare abnormal laboratory findings at each post-baseline visit.

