### **10.1.4 SAFETY DATA**

A total of 448 subjects have been exposed to reparixin in the clinical studies completed to date, of whom 337 and 112 received i.v. formulation and oral tablets, respectively. The patient population exposed to i.v. formulation includes 103 adult healthy subjects (100M/3F), 17 patients with different grades of renal impairment (12M/5F), 16 patients undergoing cardiopulmonary by pass (10M/6F), 46 patients undergoing lung transplantation (23M/23F), 48 patients undergoing kidney transplant (31M/17F), 22 undergoing liver transplant (18M/4F) and 85 receiving intrahepatic pancreatic islet infusion (32M/53F), with 22 patients in this group receiving reparixin twice. Exposure included short or prolonged i.v. infusion up to 10.6 mg/kg over 30min or 133 mg/kg over 48h and, in pancreatic islet and liver transplantation studies, 2.772 mg/kg body weight/hour i.v. continuous infusion for 7 days. Overall, reparixin was safe and well tolerated in both healthy subjects and critically ill patients. In phase 1 studies, no deaths, Serious Adverse Events (SAEs) or Adverse Event (AE)-related withdrawals were reported. The majority of AEs reported were of mild intensity. All subjects had recovered completely or had ongoing adverse events of mild intensity when they were discharged. The safety of reparixin was confirmed also in patients with different grades of renal impairment. In the interaction study no safety concerns were raised during co-administration of midazolam/tolbutamide with reparixin. During phase 2 and 3 studies, AE and SAE profile was similar for both placebo and reparixin groups and no particular safety concerns were raised. Data obtained in the trials in islet transplantation further support the safety profile of the proposed dose, even after a 7 day administration, repeated twice in several patients. Most frequent ADRs were nausea, headache, and vomiting; great majority of these were mild to moderate in nature and none required discontinuation of the Investigational Product. Tachycardia occurred in one patient from Days 5 to 38 after 1st islet infusion was judjed probable in relation to Investigational Product. Vomiting, nausea and headache on Day 5 and 6 after 2nd islet infusion in one patient and erythema, nausea and headache on Days 2 to 6 after 1st islet infusion in another patient were judged highly probable in relation to the Investigational Product. Nausea, vomiting and severe gastrointestinal bleeding associated with anaemia developed in a female patient early after the beginning of reparixin infusion because the patient received a dose of reparixin 3 times as high as that foreseen in the protocol (medical error). These events were assessed as serious by the investigator and by the Sponsor.

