4.1 General

Appropriate descriptive statistics will be produced, according to the variable:

- for continuous data n , mean, standard deviation (SD), median, Q1-Q3, and range (minimum and maximum) will be presented;
- for categorical data, frequency distributions and percentages will be presented;
- for time-to-event variables, cumulative freedom from event will be evaluated using Kaplan-Meier (KM) method. The degree of uncertainty will be expressed with 95% confidence limits (calculated per the method proposed by Greenwood³). Comparison of curves among arms will be performed with the log-rank test. KM graphs will be presented along with the number of subject-at-risk at exact time points. Subjects who have discontinued/terminated the study without an event will be censored at the date of study discontinuation/termination. Subjects ongoing and who are free from event at the time of database lock (for example at interim analyses) will be censored at the last available date.

Unless otherwise specified, hypothesis testing will be carried out at the $\alpha = 0.050$ level (two-sided) when comparing treatments. For all inferential analyses, p-value will be rounded to three decimal places. Statistical significance will be declared if the rounded p-value will be less than or equal to 0.050. For primary analysis only (section 7.1.2), p-values will be provided at 5th decimal place, in order to compare with efficacy and futility thresholds specified in section 4.5.

Additional post-hoc analysis may be produced to further allow comparison between reparixin and control, according to the results obtained. Any unplanned analyses as well as deviations from the original statistical plan will be clearly documented in the Clinical Study Report.

Derivation rules for efficacy and safety analyses are reported in Table 7 in section 9.

All the data collected and derived in the study will be presented in subject data listings by centre.

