4.9 Changes in the planned analysis

No change has been implemented in this SAP.

However, in order to clarify the analysis of the primary endpoint, a clarification of the meaning of "supplemental oxygen treatment" is provided: since all patients enrolled in this study had a respiratory distress, it is intended in all the analysis that the term "supplemental" refers to additional and/or increased oxygen requirement as compared to the baseline. In fact, all patients were expected to be already on oxygen treatment before the start of treatment. Details are provided in section 9.1.

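### SAP 8.2 leaves out two laboratory safety outputs that protocol 9.4.3 commits to, the clinically significant counts and the shift tables versus baseline, and SAP 4.9 declares no change

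*SAP*

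**What the plan says.** Protocol 9.4.3 (Safety Analysis) sets out three layers of laboratory reporting. The first is descriptive statistics by visit. The second is a count: "the frequency of subjects reporting an abnormal or abnormal clinically significant laboratory value at each available visit will be presented for each laboratory parameter". The third links each patient to baseline: "Shift tables versus baseline will compare abnormal laboratory findings at each post-baseline visit".

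SAP 8.2 (Clinical laboratory evaluation) lists two summaries for haematology and biochemistry. One is quantitative: "A summary table showing for all laboratory tests the values and changes from baseline to each subsequent time points". Under SAP 4.1, continuous data are described by n, "mean, standard deviation (SD), median, Q1-Q3, and range (minimum and maximum) will be presented". The other is the "frequency of subjects reporting laboratory values out of normal range (yes, no) at baseline and at subsequent time points".

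SAP 8.2 has no clinically significant category and no shift table. SAP 4.9 (Changes in the planned analysis) states: "No change has been implemented in this SAP". The one clarification it then adds concerns supplemental oxygen, not laboratory data.

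**The concern.** A SAP may narrow what a protocol promises, but it should say so. Here two committed safety outputs disappear while the section meant for such changes reports none. A reader of the study report would have no signal that the laboratory tables are thinner than planned.

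The omission also has a practical effect. A yes/no count at each visit is a set of separate marginal totals. It says how many patients are out of range on a given day, not who became abnormal, who recovered, or who was abnormal already and got worse. In hospitalised patients with severe pneumonia that distinction matters. Every patient must have at least one raised inflammatory marker to enter (protocol 5.2, inclusion criterion 5), so for LDH, CRP, IL-6, ferritin or XDP some abnormal baselines are built in.

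**Working it through.** There is no figure in the plan to reproduce. The check is a comparison of text, followed by a small illustration with assumed values.

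**Comparison of the two documents**

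| Laboratory output | Protocol 9.4.3 | SAP 8.2 |
|---|---|---|
| Descriptive statistics by visit | Yes | Yes, with change from baseline |
| Count of patients with abnormal values, per parameter and visit | Yes | Yes, as in or out of range |
| Count of patients with abnormal clinically significant values | Yes | Absent |
| Shift tables versus baseline, each post-baseline visit | Yes | Absent |
| Split of out-of-range values into low and high | Not promised | Absent |

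**Is the gap filled elsewhere in the SAP?** No.
- SAP 7.2.1 mentions shift tables, but as an option and only for secondary efficacy endpoints.
- Protocol section 3 lists changes in haematology values as a secondary endpoint. SAP 3.5.2 does not carry this over, so the efficacy sections do not cover haematology either.
- SAP 3.6 lists safety laboratory tests as an endpoint without adding an output.

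**What the yes/no table can and cannot show.** The protocol summary gives 32 reparixin patients in phase 2. Everything else below is assumed, purely to show the mechanism; none of it estimates a risk.

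1. *Cancellation.* Suppose 16 of 32 are out of range at baseline, 5 become abnormal and 5 recover. The later count is 16 + 5 − 5 = 16, so the table reads 16/32 both times. A shift table would show 5 normal to abnormal, 5 abnormal to normal, 16 − 5 = 11 abnormal throughout and 16 − 5 = 11 normal throughout.
2. *Reversal of direction.* A patient above range at baseline and below range later is a yes at both visits.
3. *Worsening from an abnormal baseline.* Take an assumed haemoglobin lower limit of 13 g/dL, 16 of 32 patients at 11 g/dL at baseline, and 3 of those falling by 4 g/dL with all others unchanged. The out-of-range count is 16 before and 16 after. The change-from-baseline table does move: mean 3 × 4 / 32 = 0.375 g/dL, median 0, extreme value 4.0 g/dL. It shows that a large change occurred, but not in how many patients.

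**Sign of the change.** SAP Table 7 defines change as baseline minus later value, so the falls in case 3 appear as positive numbers and the extreme is the maximum. This matters because the change table is now the main summary in which such worsening can be seen.

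**Which missing output covers which case?** Plain normal/abnormal shift tables resolve case 1. Case 2 needs a low/high split. Case 3 needs the clinically significant category, and shows only if the patient crosses from not significant to significant. A low/normal/high shift table would read low to low. Protocol 9.4.3 does not spell out the classes of its shift tables, but the sentence before it uses the clinically significant category, so carrying that category into them is the natural reading.

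**The case against.** The strongest reply is that little is hidden. The change-from-baseline table covers every laboratory test and prints the range and quartiles. SAP 4.1 provides subject listings of all collected and derived data. Under protocol 7.3.1 an abnormal laboratory finding can be an adverse event, and SAP 8.1 tabulates events by organ class, preferred term, severity and seriousness. SAP 4.6 gives the DMC laboratory summaries and longitudinal analyses. All of this stands, so a reader who infers that deterioration would leave no trace, or that the yes/no count is the only patient-level laboratory output, goes further than the documents allow. These routes do not replace the missing tables, however. The range shows an extreme and not a count, listings are not a comparison by arm, adverse events depend on investigator reporting in an open-label trial, and DMC reviews are for monitoring.

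A reader might also infer that a known bleeding and anaemia risk of reparixin would be under-reported. Protocol 10.1.4 does record that "Nausea, vomiting and severe gastrointestinal bleeding associated with anaemia developed in a female patient", but it attributes the events to an infusion given in error at three times the foreseen dose. That is one patient. The same section lists gastrointestinal haemorrhage among adverse reactions in the IV studies, but not among the frequent gastrointestinal reactions with the oral tablets, which are the phase 2 treatment. The case shows why laboratory worsening deserves tabulating. It does not establish a risk at the planned regimen.

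Two further points against a stronger reading are right. The protocol promises no low/high split, so its absence is not a departure. And the entry criteria do not select on haemoglobin or neutrophils, so the documents do not show that these are commonly abnormal at baseline.

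**Conclusion.** The point holds as an undeclared departure. SAP 8.2 drops the clinically significant counts and the shift tables that protocol 9.4.3 commits to, and SAP 4.9 says nothing changed. The abnormality table that remains cannot separate new from resolved abnormalities, cannot show a reversal of direction, and cannot show worsening from an already abnormal value.

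The consequence is moderate and confined to safety reporting. The primary analyses, the type I error and the efficacy rule for proceeding to phase 3 are untouched. No number of missed patients can be given: the documents state neither baseline abnormality rates nor an expected frequency of laboratory worsening, and the values in the illustration are assumed.

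The conclusion assumes that SAP 8.2 is meant as the full list of laboratory summaries, which is how it is written.

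**What to change.** In SAP 8.2, restore by treatment arm:

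1. shift tables from baseline to each post-baseline visit, per parameter, with the classes normal, abnormal not clinically significant and abnormal clinically significant;
2. the number of patients with abnormal clinically significant values, per parameter and visit.

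As an inexpensive addition beyond what the protocol promises, split out-of-range values into low and high.

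First check that the CRF records a clinical-significance judgement for laboratory values; the schedules of evaluations do not show one and the CRF is not among the documents. If it does not, produce low/normal/high shift tables instead and declare the departure, with the reason, in SAP 4.9. That fallback shows new, resolved and reversed abnormalities, but not a low value that falls further. If the reduction was deliberate, it belongs in SAP 4.9 in any case.

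While 8.2 is open, confirm the sign convention for change from baseline in SAP Table 7.

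The cost is a few more tables. Haematology, including the predefined blood chemistry, is already scheduled at every visit (protocol 11.2, SAP Table 1), so no new sampling is needed.

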8.3 Vital signs

Summary statistics by treatment will be provided at each available time point:

- Weight (Kg),
- Height (cm) if applicable,
- Systolic Blood Pressure (mmHg),
- Diastolic Blood Pressure (mmHg),
- Heart Rate (bpm),
- Body temperature (°C),
- Respiration Rate (breath / min)

8.4 Pregnancy test over the study

A summary table showing test results (Negative/Positive) over the study will be produced by treatment group, where applicable.

9. Derivations and date conventions

9.1 Variable derivation

Table 7: Variable derivation rules

Parameter	Derivation
ARDS Severity classification based on PaO₂/FiO₂	
According to PaO₂/FiO₂ (RESPIRATORY PARAMETERS form) the classification is:
 
 • if $200 \leq \text{PaO}_2/\text{FiO}_2 < 300$ mmHg then ARDS Severity=Mild • if $100 \leq \text{PaO}_2/\text{FiO}_2 < 200$ mmHg then ARDS Severity=Moderate • if $\text{PaO}_2/\text{FiO}_2 < 100$ mmHg then ARDS Severity=Severe
Worsening based on PaO₂/FiO₂	
A patient with ARDS ($\text{PaO}_2/\text{FiO}_2 < 300$ mmHg) is considered “Worsened” in case of a decrease of PaO₂/FiO₂ of at least one third (-33,3%) from the baseline PaO₂/FiO₂ value.

Oxygen Delivery System Classification based on type of oxygen support	
According to Type of oxygen support (RESPIRATORY PARAMETERS form) the classification is:
 
 • If “Invasive Medicinal Ventilation” or “ECMO” then Class=Invasive • Else if “High Flow Nasal Cannula” or “BIPAP or CPAP” then Class=High Flow • Else if “Nasal Cannula” or “Mask” then Class=Low Flow
Worsening based on Oxygen Delivery System Classification	
A patient is considered “Worsened” after baseline if he/she increase the level of severity within the oxygen delivery system classification (Invasive > High Flow > Low Flow).

Last available date (for censoring time-to-event analysis)	
Last date will be considered as the most recent dates collect in:
 
 • Last assessment, • Start and stop dates of AEs 
Last date = max (date of last assessment, start AEs, Stop AEs)

Parameter	Derivation
Composite endpoint of phase 2 and Time to event (days)	
From ADDITIONAL INFORMATION form:
 
 • if “Has the patient been admitted to the ICU?” = “Yes”, then component1 = “Yes” and date of event1 = Date of Visit • if “Has the patient been admitted to the ICU?” = “No”, then component1 = “No” 
From PATIENT STATUS form:
 
 • if “Is the subject eligible to switch to rescue medication?” = “Yes”, then component2 = “Yes” and date of event2 = Rescue treatment start date 
 ○ If Rescue treatment start date is missing, then Date of Visit will be used • if “Is the subject eligible to switch to rescue medication?” = “No”, then component2 = “No” 
From ADDITIONAL INFORMATION and MECHANICAL VENTILATION forms:
 
 • If “Has the patient been mechanically ventilated?” = “Yes” and type = “Invasive mechanical ventilation”, then component3 = “Yes” and date of event3 = mechanical ventilation start date 
 ○ If mechanical ventilation start date is missing, then Date of Visit will be used • If “Has the patient been mechanically ventilated?” is not empty and type ≠ “Invasive mechanical ventilation”, then component3 = “No” 
From “Worsening based on PaO₂/FiO₂” (see above):
 
 • if a patient is classified as “Worsened”, then component4 = “Yes” and date of event4 = Date of Visit • if a patient is classified as not “Worsened” (excluding missing classification), then component4 = “No” 
The composite endpoint is equal to “Yes” if at least one post-baseline component (1-4) is equal to “Yes” and the date of event is the corresponding date of event. In case of more component equal to “Yes”, the first date will be used.
 
Otherwise, if all component (1-4) are equal to “No” the composite endpoint will set as “No”. The date of event will be last date where is known that all components are equal to “No”.
 
Time to composite endpoint (days) = Date of event - Date of randomization

Parameter	Derivation

Modified Composite endpoint of phase 2 and Time to event (days) [sensitivity analysis]
	
From ADDITIONAL INFORMATION form:
 
 • if “Has the patient been admitted to the ICU?” = “Yes”, then component1 = “Yes” and date of event1 = Date of Visit • if “Has the patient been admitted to the ICU?” = “No”, then component1 = “No” 
From PATIENT STATUS form:
 
 • if “Is the subject eligible to switch to rescue medication?” = “Yes”, then component2 = “Yes” and date of event2 = Rescue treatment start date 
 ○ If Rescue treatment start date is missing, then Date of Visit will be used • if “Is the subject eligible to switch to rescue medication?” = “No”, then component2 = “No” 
From ADDITIONAL INFORMATION and MECHANICAL VENTILATION forms:
 
 • If “Has the patient been mechanically ventilated?” = “Yes” and type = “Invasive mechanical ventilation”, then component3 = “Yes” and date of event3 = mechanical ventilation start date 
 ○ If mechanical ventilation start date is missing, then Date of Visit will be used • If “Has the patient been mechanically ventilated?” is not empty and type ≠ “Invasive mechanical ventilation”, then component3 = “No” 
From “Worsening based on PaO2/FiO2” (see above):
 
 • if a patient is classified as “Worsened”, then component4 = “Yes” and date of event4 = Date of Visit • if a patient is classified as not “Worsened” (excluding missing classification), then component4 = “No” 
From DEATH REPORT form:
 
 • If “Date of death” is not missing, then component5 = “Yes” and date of event5 = date of death • Otherwise component5 = “No” 
The composite endpoint is equal to “Yes” if at least one post-baseline component (1-5) is equal to “Yes” and the date of event is the corresponding date of event. In case of more component equal to “Yes”, the first date will be used.
 
Otherwise, if all component (1-4) are equal to “No” the composite endpoint will set as “No”. The date of event will be last date where is known that all components are equal to “No”.
 
Time to composite endpoint (days) = Date of event - Date of randomization

Parameter	Derivation

Composite endpoint of phase 3 and time to event (days)
	
From ADDITIONAL INFORMATION form:
 
 • if “Has the patient been admitted to the ICU?” = “Yes”, then component1 = “Yes” and date of event1 = Date of Visit • if “Has the patient been admitted to the ICU?” = “No”, then component1 = “No” 
From ADDITIONAL INFORMATION and MECHANICAL VENTILATION forms:
 
 • If “Has the patient been mechanically ventilated?” = “Yes” and type = “Invasive mechanical ventilation”, then component3 = “Yes” and date of event3 = mechanical ventilation start date 
 ○ If mechanical ventilation start date is missing, then Date of Visit will be used • If “Has the patient been mechanically ventilated?” is not empty and type ≠ “Invasive mechanical ventilation”, then component3 = “No” 
From DEATH REPORT form:
 
 • If “Date of death” is not missing, then component5 = “Yes” and date of event5 = date of death • Otherwise component5 = “No” 
The composite endpoint is equal to “Yes” if at least one post-baseline component (1, 3 and 5) is equal to “Yes” and the date of event is the corresponding date of event. In case of more component equal to “Yes”, the first date will be used.
 
Otherwise, if all component (1, 3) are equal to “No” the composite endpoint will set as “No”. The date of event will be last date where is known that all components are equal to “No”.
 
Time to composite endpoint (days) = Date of event - Date of randomization

Parameter	Derivation
Composite endpoint of phase 2 and Time to event (days) using Oxygen Delivery System Classification	
From ADDITIONAL INFORMATION form:
 
 • if “Has the patient been admitted to the ICU?” = “Yes”, then component1 = “Yes” and date of event1 = Date of Visit • if “Has the patient been admitted to the ICU?” = “No”, then component1 = “No” 
From PATIENT STATUS form:
 
 • if “Is the subject eligible to switch to rescue medication?” = “Yes”, then component2 = “Yes” and date of event2 = Rescue treatment start date 
 ○ If Rescue treatment start date is missing, then Date of Visit will be used • if “Is the subject eligible to switch to rescue medication?” = “No”, then component2 = “No” 
From ADDITIONAL INFORMATION and MECHANICAL VENTILATION forms:
 
 • If “Has the patient been mechanically ventilated?” = “Yes” and type = “Invasive mechanical ventilation”, then component3 = “Yes” and date of event3 = mechanical ventilation start date 
 ○ If mechanical ventilation start date is missing, then Date of Visit will be used • If “Has the patient been mechanically ventilated?” is not empty and type ≠ “Invasive mechanical ventilation”, then component3 = “No” 
From “Worsening based on Oxygen Delivery System Classification” (see above):
 
 • if a patient is classified as “Worsened”, then component4 = “Yes” and date of event4 = Date of Visit • if a patient is classified as not “Worsened” (excluding missing classification), then component4 = “No” 
The composite endpoint is equal to “Yes” if at least one post-baseline component (1-4) is equal to “Yes” and the date of event is the corresponding date of event. In case of more component equal to “Yes”, the first date will be used.
 
Otherwise, if all component (1-4) are equal to “No” the composite endpoint will set as “No”. The date of event will be last date where is known that all components are equal to “No”.
 
Time to composite endpoint (days) = Date of event - Date of randomization

Time from randomization to discontinuation (days)	Time from randomization to discontinuation (days) = Date of study withdrawal – Date of randomization
Extent of exposure (days)	Extent of exposure (days) = Date of last drug administration - Date of first drug administration

Parameter	Derivation
Time to supplemental oxygen requirement (days)	Time to supplemental oxygen requirement (days) = First Administration start date - Date of randomization
Time to mechanical invasive ventilation use (days)	Time to (invasive) mechanical ventilation use (days) = First (invasive) Mechanical Ventilation start date - Date of randomization
Time to admission to ICU (days)	Time to admission to ICU (days) = Admission date - Date of randomization
Time to rescue medication (days)	Time to rescue medication (days) = First rescue treatment start date - Date of randomization
Overall survival (days)	Overall survival (days) = Date of death - Date of randomization
Subject with improvement based on Likert scale	Improvement = any of these answers: 
 • 1 = minimally better, • 2 = moderately better, and • 3 = markedly better
Cumulative quantity (L) of oxygen treatment	Cumulative quantity of oxygen treatment (L) = Sum of all Quantity (L) in CONCOMITANT OXYGEN TREATMENT form, from randomization to time point of interest. It is defined as supplemental oxygen requirement any increased used of oxygen compared to baseline.
Cumulative duration (hours) of oxygen treatment	Cumulative duration of oxygen treatment (hours) = Sum of duration of oxygen administration (hours) in CONCOMITANT OXYGEN TREATMENT form, from randomization to time point of interest. Duration of oxygen administration (hours) = Administration end date/time - Administration start date/time / 60
Cumulative duration (hours) of mechanical ventilation	Cumulative duration of mechanical ventilation (hours) = Sum of duration of mechanical ventilation (hours) in MECHANICAL VENTILATION form, from randomization to time point of interest. Duration of mechanical ventilation (hours) = End date/time - Start date/time / 60
Duration (days) of ICU stay	Duration of ICU stay (days) = Discharge date - Admission date
Change from baseline	For changes from baseline the baseline value will constitute the minuend and the later value the subtrahend.
Conversion of Time Intervals	If a time interval was calculated in minutes, hours or days and needs to be converted into months or years the following conversion factors will be used: 
 • 1 hour = 60 minutes • 1 day = 24 hours • 1 week = 7 days • 1 month = 30.4375 days • 1 year = 365.25 days

